11 APPENDICES

[Appendix A: Efficacy Endpoint Summary Table](#)

[Appendix B: Schedule of Events](#)

[Appendix C: Gastrointestinal Standardized MedDRA Query](#)

[Appendix D: SAS Code for Primary Statistical Analysis](#)

APPENDIX A EFFICACY ENDPOINT SUMMARY TABLE

Test / Instrument	Eligible Study Population	Endpoint	Subjects Applicable	Endpoint Level	Timepoints for Assessments	Statistical Approach: Week 8 Analyses	Statistical Approach: Week 52 Analyses
Seizure Diary + EEG	Efficacy Analysis Set	Reduction from baseline in frequency of seizures	All	Primary	Diary: daily from Screening to 52/ET; EEG: Screening, Randomization, Week 8, 26, 31	ANCOVA	Estimation
Seizure Diary + EEG	Efficacy Analysis Set	Seizure response	All	Secondary	Diary: daily from Screening to 52/ET; EEG: Screening, Randomization, Week 8, 26, 31	Logistic Regression	Estimation
Seizure Diary	Efficacy Analysis Set – Observable Seizures	Reduction from baseline in frequency of observable seizures	All	Secondary	Daily from Screening to 52/ET	ANCOVA	Estimation
Seizure Diary	Efficacy Analysis Set – Observable Seizures	Observable seizure response	All	Secondary	Daily from Screening to 52/ET	Logistic Regression	Estimation
EEG	Efficacy Analysis Set – Absence Seizures	Reduction from baseline in frequency of absence seizures	All	Secondary	Screening, Randomization, Week 8, 26, 31	ANCOVA	Estimation
EEG	Efficacy Analysis Set – Absence Seizures	Absence seizure response	All	Secondary	Screening, Randomization, Week 8, 26, 31	Logistic Regression	Estimation
CANTAB	Efficacy Analysis Set	Change from baseline in CANTAB RTI Simple Choice Median Reaction Time (RTIMDSRT)	All	Secondary	Screening, Randomization, Week 4, 8, 26, 31, 36, 52, ET	GEE Linear	Estimation

Test / Instrument	Eligible Study Population	Endpoint	Subjects Applicable	Endpoint Level	Timepoints for Assessments	Statistical Approach: Week 8 Analyses	Statistical Approach: Week 52 Analyses
CANTAB	Efficacy Analysis Set	Change from baseline in CANTAB RTI Five Choice Median Reaction Time (RTIMDFRT)	All	Secondary	Screening, Randomization, Week 4, 8, 26, 31, 36, 52, ET	GEE Linear	Estimation
CANTAB	Efficacy Analysis Set	Change from baseline in CANTAB RTI Simple Choice Standard Deviation (RTISRSD)	All	Secondary	Screening, Randomization, Week 4, 8, 26, 31, 36, 52, ET	GEE Linear	Estimation
CANTAB	Efficacy Analysis Set	Change from baseline in CANTAB SSP Span Length (SSPSLF)	All	Secondary	Screening, Randomization, Week 4, 8, 26, 31, 36, 52, ET	GEE Linear	Estimation
CANTAB	Efficacy Analysis Set	Change from baseline in CANTAB PAL Total Errors (Adjusted) (PALTEA)	All	Secondary	Screening, Randomization, Week 4, 8, 26, 31, 36, 52, ET	GEE Linear	Estimation
CANTAB	Efficacy Analysis Set	Change from baseline in CANTAB PAL First Trial Memory Score (PALFTMS)	All	Secondary	Screening, Randomization, Week 4, 8, 26, 31, 36, 52, ET	GEE Linear	Estimation
CANTAB	Efficacy Analysis Set	Change from baseline in CANTAB SWM Between Errors (SWMBE48)	All	Secondary	Screening, Randomization, Week 4, 8, 26, 31, 36, 52, ET	GEE Linear	Estimation
CANTAB	Efficacy Analysis Set	Change from baseline in CANTAB SWM Strategy (SWMS68)	All	Secondary	Screening, Randomization, Week 4, 8, 26, 31, 36, 52, ET	GEE Linear	Estimation
6-minute walk test (6MWT)	Efficacy Analysis Set	Change from baseline in 6MWT distance traveled (in meters)	All	Secondary	Screening, Randomization, Week 4, 8, 26, 31, 36, 52, ET	GEE Linear	Estimation

Test / Instrument	Eligible Study Population	Endpoint	Subjects Applicable	Endpoint Level	Timepoints for Assessments	Statistical Approach: Week 8 Analyses	Statistical Approach: Week 52 Analyses
6-minute walk test (6MWT)	Efficacy Analysis Set	Change from baseline in 6MWT distance traveled (in percent predicted)	All	Secondary	Screening, Randomization, Week 4, 8, 26, 31, 36, 52, ET	GEE Linear	Estimation
6-minute walk test (6MWT)	Efficacy Analysis Set	Time (in minutes) to onset of paroxysmal exertional dyskinesia (PED)	All	Secondary	Screening, Randomization, Week 4, 8, 26, 31, 36, 52, ET	GEE Logistic	Estimation
GMFM-88	Efficacy Analysis Set	Change from baseline in GMFM-88 Total score	Select Sites	Secondary	Randomization, Week 4, 8, 26, 31, 36, 52, ET	GEE Linear	Estimation
Seizure Diary	Efficacy Analysis Set – Observable Seizures	Reduction from baseline in frequency of generalized tonic-clonic seizures	All	Exploratory	Daily from Screening to 52/ET	Summary Statistics	Summary Statistics
Seizure Diary	Efficacy Analysis Set – Observable Seizures	Reduction from baseline in frequency of generalized tonic seizures	All	Exploratory	Daily from Screening to 52/ET	Summary Statistics	Summary Statistics
Seizure Diary	Efficacy Analysis Set – Observable Seizures	Reduction from baseline in frequency of generalized clonic seizures	All	Exploratory	Daily from Screening to 52/ET	Summary Statistics	Summary Statistics
Seizure Diary	Efficacy Analysis Set – Observable Seizures	Reduction from baseline in frequency of generalized atonic seizures	All	Exploratory	Daily from Screening to 52/ET	Summary Statistics	Summary Statistics

Test / Instrument	Eligible Study Population	Endpoint	Subjects Applicable	Endpoint Level	Timepoints for Assessments	Statistical Approach: Week 8 Analyses	Statistical Approach: Week 52 Analyses
Seizure Diary	Efficacy Analysis Set – Observable Seizures	Reduction from baseline in frequency of partial/focal with secondary generalization seizures	All	Exploratory	Daily from Screening to 52/ET	Summary Statistics	Summary Statistics
Seizure Diary	Efficacy Analysis Set – Observable Seizures	Reduction from baseline in frequency of myoclonic seizures	All	Exploratory	Daily from Screening to 52/ET	Summary Statistics	Summary Statistics
Seizure Diary	Efficacy Analysis Set – Observable Seizures	Reduction from baseline in frequency of myoclonic atonic seizures	All	Exploratory	Daily from Screening to 52/ET	Summary Statistics	Summary Statistics
Seizure Diary	Efficacy Analysis Set – Observable Seizures	Reduction from baseline in frequency of myoclonic tonic seizures	All	Exploratory	Daily from Screening to 52/ET	Summary Statistics	Summary Statistics
Seizure Diary	Efficacy Analysis Set – Observable Seizures	Reduction from baseline in frequency of complex partial/focal seizures	All	Exploratory	Daily from Screening to 52/ET	Summary Statistics	Summary Statistics
Seizure Diary	Efficacy Analysis Set – Observable Seizures	Reduction from baseline in frequency of simple partial/focal motor seizures	All	Exploratory	Daily from Screening to 52/ET	Summary Statistics	Summary Statistics
Seizure Diary	Efficacy Analysis Set – Observable Seizures	Reduction from baseline in frequency of simple partial/focal sensory seizures	All	Exploratory	Daily from Screening to 52/ET	Summary Statistics	Summary Statistics

Test / Instrument	Eligible Study Population	Endpoint	Subjects Applicable	Endpoint Level	Timepoints for Assessments	Statistical Approach: Week 8 Analyses	Statistical Approach: Week 52 Analyses
Seizure Diary	Efficacy Analysis Set – Observable Seizures	Reduction from baseline in frequency of simple partial/focal psychological seizures	All	Exploratory	Daily from Screening to 52/ET	Summary Statistics	Summary Statistics
Seizure Diary	Efficacy Analysis Set – Observable Seizures	Reduction from baseline in frequency of typical absence seizures	All	Exploratory	Daily from Screening to 52/ET	Summary Statistics	Summary Statistics
Seizure Diary	Efficacy Analysis Set – Observable Seizures	Reduction from baseline in frequency of atypical absence seizures	All	Exploratory	Daily from Screening to 52/ET	Summary Statistics	Summary Statistics
Seizure Diary	Efficacy Analysis Set – Observable Seizures	Reduction from baseline in frequency of myoclonic absence seizures	All	Exploratory	Daily from Screening to 52/ET	Summary Statistics	Summary Statistics
Seizure Diary	Efficacy Analysis Set – Observable Seizures	Reduction from baseline in frequency of absence eyelid myoclonia seizures	All	Exploratory	Daily from Screening to 52/ET	Summary Statistics	Summary Statistics
Seizure Diary	Efficacy Analysis Set – Observable Seizures	Reduction from baseline in frequency of unclassified seizures including epileptic spasms	All	Exploratory	Daily from Screening to 52/ET	Summary Statistics	Summary Statistics
CNS	Efficacy Analysis Set	Change from baseline in CNS Total Score	All	Exploratory	Randomization, Week 8, 26, 52, ET	Summary Statistics	Summary Statistics

Test / Instrument	Eligible Study Population	Endpoint	Subjects Applicable	Endpoint Level	Timepoints for Assessments	Statistical Approach: Week 8 Analyses	Statistical Approach: Week 52 Analyses
CGI-I	Efficacy Analysis Set	CGI Improvement scale	All	Exploratory	Randomization, Week 8, 26, 31, 36, 52, ET	Summary Statistics	Summary Statistics
SF-10	Efficacy Analysis Set	Change from baseline in SF-10 Physical Summary Score (PHS-10)	Ages 5-17	Exploratory	Randomization, Week 8, 26, 52, ET	Summary Statistics	Summary Statistics
SF-10	Efficacy Analysis Set	Change from baseline in SF-10 Psychosocial Summary Score (PSS-10)	Ages 5-17	Exploratory	Randomization, Week 8, 26, 52, ET	Summary Statistics	Summary Statistics
SF-12 v2	Efficacy Analysis Set	Change from baseline in Physical Functioning (PF) score	Ages 18+	Exploratory	Randomization, Week 8, 26, 52, ET	Summary Statistics	Summary Statistics
SF-12 v2	Efficacy Analysis Set	Change from baseline in Role Limitations due to Physical Health (RP) score	Ages 18+	Exploratory	Randomization, Week 8, 26, 52, ET	Summary Statistics	Summary Statistics
SF-12 v2	Efficacy Analysis Set	Change from baseline in Bodily Pain (BP) score	Ages 18+	Exploratory	Randomization, Week 8, 26, 52, ET	Summary Statistics	Summary Statistics
SF-12 v2	Efficacy Analysis Set	Change from baseline in General Health Perceptions (GH) score	Ages 18+	Exploratory	Randomization, Week 8, 26, 52, ET	Summary Statistics	Summary Statistics

Test / Instrument	Eligible Study Population	Endpoint	Subjects Applicable	Endpoint Level	Timepoints for Assessments	Statistical Approach: Week 8 Analyses	Statistical Approach: Week 52 Analyses
SF-12 v2	Efficacy Analysis Set	Change from baseline in Vitality (VT) score	Ages 18+	Exploratory	Randomization, Week 8, 26, 52, ET	Summary Statistics	Summary Statistics
SF-12 v2	Efficacy Analysis Set	Change from baseline in Social Functioning (SF) score	Ages 18+	Exploratory	Randomization, Week 8, 26, 52, ET	Summary Statistics	Summary Statistics
SF-12 v2	Efficacy Analysis Set	Change from baseline in Role Limitations due to Emotions Problems (RE) score	Ages 18+	Exploratory	Randomization, Week 8, 26, 52, ET	Summary Statistics	Summary Statistics
SF-12 v2	Efficacy Analysis Set	Change from baseline in Mental Health (MH) score	Ages 18+	Exploratory	Randomization, Week 8, 26, 52, ET	Summary Statistics	Summary Statistics
SF-12 v2	Efficacy Analysis Set	Change from baseline in Physical Component Summary Scale (PCS-12)	Ages 18+	Exploratory	Randomization, Week 8, 26, 52, ET	Summary Statistics	Summary Statistics
SF-12 v2	Efficacy Analysis Set	Change from baseline in Mental Component Summary Scale (MCS-12)	Ages 18+	Exploratory	Randomization, Week 8, 26, 52, ET	Summary Statistics	Summary Statistics
PPVT	Efficacy Analysis Set	Change from baseline in PPVT standardized score	Select Sites	Exploratory	Screening, Week 8, 26, 31, 36, 52, ET	Summary Statistics	Summary Statistics

Test / Instrument	Eligible Study Population	Endpoint	Subjects Applicable	Endpoint Level	Timepoints for Assessments	Statistical Approach: Week 8 Analyses	Statistical Approach: Week 52 Analyses
PEDI-CAT	Efficacy Analysis Set	Change from baseline in Daily Activities score	Select Sites	Exploratory	Randomization, Week 4, 8, 26, 31, 36, 52, ET	Data Listing	Data Listing
PEDI-CAT	Efficacy Analysis Set	Change from baseline in Mobility score	Select Sites	Exploratory	Randomization, Week 4, 8, 26, 31, 36, 52, ET	Data Listing	Data Listing
PEDI-CAT	Efficacy Analysis Set	Change from baseline in Social/Cognitive score	Select Sites	Exploratory	Randomization, Week 4, 8, 26, 31, 36, 52, ET	Data Listing	Data Listing
PEDI-CAT	Efficacy Analysis Set	Change from baseline in Responsibility score	Select Sites	Exploratory	Randomization, Week 4, 8, 26, 31, 36, 52, ET	Data Listing	Data Listing
Gait analysis during 6-minute walk test (6MWT)	Efficacy Analysis Set	Change from baseline in stride length	Select Sites	Exploratory	Screening, Randomization, Week 4, 8, 26, 31, 36, 52, ET	Data Listing	Data Listing
Gait analysis during 6-minute walk test (6MWT)	Efficacy Analysis Set	Change from baseline in velocity	Select Sites	Exploratory	Screening, Randomization, Week 4, 8, 26, 31, 36, 52, ET	Data Listing	Data Listing
Gait analysis during 6-minute walk test (6MWT)	Efficacy Analysis Set	Change from baseline in cadence	Select Sites	Exploratory	Screening, Randomization, Week 4, 8, 26, 31, 36, 52, ET	Data Listing	Data Listing

Test / Instrument	Eligible Study Population	Endpoint	Subjects Applicable	Endpoint Level	Timepoints for Assessments	Statistical Approach: Week 8 Analyses	Statistical Approach: Week 52 Analyses
Gait analysis during 6-minute walk test (6MWT)	Efficacy Analysis Set	Change from baseline in base of support	Select Sites	Exploratory	Screening, Randomization, Week 4, 8, 26, 31, 36, 52, ET	Data Listing	Data Listing
Gait analysis during 6-minute walk test (6MWT)	Efficacy Analysis Set	Change from baseline in percentage of cycle time spent in double support	Select Sites	Exploratory	Screening, Randomization, Week 4, 8, 26, 31, 36, 52, ET	Data Listing	Data Listing
GMFM-88	Efficacy Analysis Set	Change from baseline in GMFM-88 Lying and Rolling score	Select Sites	Secondary	Randomization, Week 4, 8, 26, 31, 36, 52, ET	Data Listing	Data Listing
GMFM-88	Efficacy Analysis Set	Change from baseline in GMFM-88 Sitting score	Select Sites	Secondary	Randomization, Week 4, 8, 26, 31, 36, 52, ET	Data Listing	Data Listing
GMFM-88	Efficacy Analysis Set	Change from baseline in GMFM-88 Crawling and Kneeling score	Select Sites	Secondary	Randomization, Week 4, 8, 26, 31, 36, 52, ET	Data Listing	Data Listing
GMFM-88	Efficacy Analysis Set	Change from baseline in GMFM-88 Standing score	Select Sites	Secondary	Randomization, Week 4, 8, 26, 31, 36, 52, ET	Data Listing	Data Listing
GMFM-88	Efficacy Analysis Set	Change from baseline in GMFM-88 Walking, Running and Jumping score	Select Sites	Secondary	Randomization, Week 4, 8, 26, 31, 36, 52, ET	Data Listing	Data Listing

Test / Instrument	Eligible Study Population	Endpoint	Subjects Applicable	Endpoint Level	Timepoints for Assessments	Statistical Approach: Week 8 Analyses	Statistical Approach: Week 52 Analyses
Beery-VMI	Efficacy Analysis Set	Change from baseline in standard score	Select Sites	Exploratory	Screening, Week 8, 26, 52, ET	Data Listing	Data Listing
RCPM	Efficacy Analysis Set	Change from baseline in total score	Select Sites	Exploratory	Screening, Week 8, 26, 52, ET	Data Listing	Data Listing

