5.6 Classification of Subjects at Randomization by Seizure Type

Classification of subjects is used to derive the primary efficacy endpoint and to define which subjects are included in secondary endpoint analyses of specific seizure types. At the Randomization Visit, subjects can be classified according to the types of seizures that are recorded on the diary as follows:

- **Observable Seizures Subject:** a subject who meets any of the following:
 - Observable Seizure Frequency (types A, B, C, D, E, F, G, H, I, J, K and L; see Section 5.7.5) greater than or equal to 4 at Randomization
 - Observable Seizure Frequency less than 4 at Randomization and Absence Seizure Frequency less than 4 at Randomization
- **Absence Seizures Subject:** a subject who meets any of the following:
 - has seizure types M, N, O or P (see Section 5.7.5) recorded on the seizure diary during the Baseline Period
 - has absence seizures documented on the Screening EEG
 - Absence Seizure Frequency (see Section 5.7.2) greater than 0 at Randomization

All subjects will either be an Observable Seizures Subject, an Absence Seizures Subject, or both. Since there is potential overlap, the following definitions are used to classify randomized subjects into three mutually exclusive groups:

- **Observable Seizures Only Subject:** a subject who is an Observable Seizures Subject *but not an Absence Seizure Subject*
- **Absence Seizures Only Subject:** a subject who is an Absence Seizures Subject *but not an Observable Seizure Subject*
- **Both Seizures Subject:** a subject who is both an Observable Seizures Subject and an Absence Seizure Subject

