6.3.1 Efficacy Analysis Set – Observable Seizures

The Efficacy Analysis Set – Observable Seizures is the subset of subjects in the Efficacy Analysis Set who are Observable Seizures Subjects (see Section 5.6).

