Table	CANTAB Spatial Working Memory Strategy – Week 8 Analysis – Summary – Efficacy Analysis Set – CANTAB
Table	CANTAB – Change from Baseline – Week 8 Analysis – GEE – Efficacy Analysis Set – CANTAB
Table	CANTAB – Change from Baseline – Week 8 Analysis – GEE – Per Protocol Analysis Set – CANTAB
Table	6MWT Distance (meters) – Week 8 Analysis – Summary – Efficacy Analysis Set – 6MWT
Table	6MWT Distance (percent predicted) – Week 8 Analysis – Summary – Efficacy Analysis Set – 6MWT
Table	Onset of PED – Week 8 Analysis – Summary – Efficacy Analysis Set – 6MWT

Output Type	Title
Table	6MWT – Change from Baseline – Week 8 Analysis – GEE – Efficacy Analysis Set – 6MWT
Table	Onset of PED – Week 8 Analysis – GEE – Efficacy Analysis Set – 6MWT
Table	GMFM-88 Total Score – Week 8 Analysis – Summary – Efficacy Analysis Set – GMFM-88
Table	GMFM-88 Total Score – Change from Baseline – Week 8 Analysis – GEE – Efficacy Analysis Set – GMFM-88
	Exploratory Efficacy Analyses
Table	Frequency of Seizure Types via Diary – Week 8 Analysis – Summary – Efficacy Analysis Set
Table	Frequency of Seizure Types via EEG – Week 8 Analysis – Summary – Efficacy Analysis Set
Table	CGI-S and CGI-I – Week 8 Analysis – Summary – Efficacy Analysis Set – CGI-I
Table	CGI-I – Week 8 Analysis – t-tests – Efficacy Analysis Set
Table	SF-10 – Week 8 Analysis – Summary – Efficacy Analysis Set – SF-10
Table	SF-12 v2 – Week 8 Analysis – Summary – Efficacy Analysis Set – SF-12
Table	SF-10 – Change from Baseline – Week 8 Analysis – t-tests – Efficacy Analysis Set
Table	SF-12 – Change from Baseline – Week 8 Analysis – t-tests – Efficacy Analysis Set
Table	CNS – Week 8 Analysis – Summary – Efficacy Analysis Set – CNS
Table	CNS – Change from Baseline – Week 8 Analysis – t-tests – Efficacy Analysis Set
	Safety Analyses of Adverse Events
Table	Overall Summary of Adverse Events – Safety Analysis Set
Table	Overall Summary of Adverse Events by Study Period – Safety Analysis Set
Table	Treatment Emergent Adverse Events by System Organ Class and Preferred Term – Safety Analysis Set
Table	Serious Treatment Emergent Adverse Events by System Organ Class and Preferred Term – Safety Analysis Set
Table	Treatment Emergent Adverse Events by System Organ Class, Preferred Term and Greatest Severity – Safety Analysis Set
Table	Treatment Emergent Adverse Events by System Organ Class, Preferred Term and Greatest Reported Relationship – Safety Analysis Set

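### SAP Appendix A puts the four diary absence-seizure endpoints in the Observable Seizures set, which leaves out every Absence Seizures Only Subject and conflicts with Table 6

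*SAP*

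**What the plan says.** SAP Appendix A has 17 exploratory rows for seizure types recorded in the diary. Four concern absence seizures: typical ("Reduction from baseline in frequency of typical absence seizures"), atypical ("Reduction from baseline in frequency of atypical absence seizures"), myoclonic absence and eyelid myoclonia. Each gives the eligible population as "Efficacy Analysis Set – Observable Seizures", marks all subjects as applicable, and plans summary statistics at Week 8 and Week 52.

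SAP 6.3.1 defines that population: it "is the subset of subjects in the Efficacy Analysis Set who are Observable Seizures Subjects". SAP 5.6 gives two ways to be an Observable Seizures Subject. One is an observable seizure frequency (types A to L) "greater than or equal to 4 at Randomization". The other is "Observable Seizure Frequency less than 4 at Randomization and Absence Seizure Frequency less than 4 at Randomization". An Absence Seizures Only Subject is an Absence Seizures Subject who meets neither.

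Other parts of the SAP point elsewhere:

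- Table 6 (Section 9) plans "Frequency of Seizure Types via Diary – Week 8 Analysis – Summary – Efficacy Analysis Set", with no subset named.
- Section 8.6.5 promises summary statistics by visit for diary seizure types, with between-group p-values for the double-blind period, and names no analysis set.
- The EEG absence rows of Appendix A use the Absence Seizures set.

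**The concern.** An endpoint about absence seizures is assigned to a set that is defined by observable seizures and shuts out the subjects classified on absence seizures alone. Table 2 does not count codes M to P as observable seizures. The row for unclassified seizures, which Table 2 does not count as observable either, carries the same set, so the cell may simply have been repeated down all 17 diary rows.

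Two things are at stake. At Week 8 the SAP supports two different populations, and so two possible p-values, for the same diary comparison, with nothing to say which governs. After Week 31 the schedule has no further EEG, while the diary runs to Week 52, so the diary is then the only absence record. Table 6 lists no Week 52 output for diary seizure types that would override Appendix A.

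**Working it through.** There is no stated figure to reproduce; the question is one of set membership.

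**Inputs (SAP 5.6, 5.7.1, 5.7.2).** Let O be the observable seizure frequency at randomization (per 4 weeks) and E the EEG absence frequency at randomization (per 24 hours).

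- Observable Seizures Subject: O ≥ 4, or (O < 4 and E < 4).
- Absence Seizures Subject: any diary code M to P in the Baseline Period, or absence seizures on the Screening EEG, or E > 0.
- Absence Seizures Only Subject: the second but not the first.

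**Step 1.** Negating the first rule leaves exactly O < 4 and E ≥ 4.

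**Step 2.** E ≥ 4 implies E > 0, so everyone in Step 1 is an Absence Seizures Subject. Absence Seizures Only therefore means O < 4 and E ≥ 4.

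**Step 3.** The set in 6.3.1 holds only Observable Seizures Subjects, so its overlap with Absence Seizures Only is empty.

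**Check by enumeration.** Six values of O (0, 1, 3.9, 4, 8, 20), six of E (0, 1, 3.9, 4, 8, 50), diary absence yes/no and Screening EEG absence yes/no give 6 × 6 × 2 × 2 = 144 combinations.

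- Absence Seizures Only: 3 values of O below 4 × 3 values of E at or above 4 × 4 = 36.
- Observable Seizures Only: E = 0 with neither absence indicator, for 6 values of O = 6.
- Both: 144 − 36 − 6 = 102.
- Absence Seizures Only combinations inside the Observable Seizures set: 0 of 36.

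These are counts of rule combinations, not expected patient numbers.

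**Populations that could apply to the diary absence endpoints**

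| Source | Population | Includes Absence Seizures Only? |
|---|---|---|
| Appendix A, eligible population | Observable Seizures set | No |
| Appendix A, subjects applicable | All | Yes |
| Table 6, Week 8 | Efficacy Analysis Set | Yes |
| Section 8.6.5 | None named | Not stated |
| Section 8.1, open-label period | Extension Set | Yes, if they continued |

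**Illustrative size.** The documents give no share of Absence Seizures Only Subjects. Assuming 20% to 40% of 40 subjects: 0.20 × 40 = 8 to 0.40 × 40 = 16. At 3:1 allocation, one quarter would be on placebo: about 2 to 4, out of roughly 40 / 4 = 10. This ignores the first three subjects, who were randomized 1:1.

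**The case against.** The strongest reply is that the exclusion may never happen. Table 6 lists the outputs to be produced and puts the Week 8 summary on the full Efficacy Analysis Set. Section 8.1 names the Efficacy or Per Protocol set for the double-blind period and the Extension Set for the open-label period. A by-type diary listing covers the Randomized Population. This stands as far as it goes: nobody is dropped where those sections govern. But the SAP does not rank them above Appendix A, which Section 8.6 presents as the more thorough table, so the contradiction remains.

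It is also fair that these rows are exploratory and that no confirmatory claim rests on them.

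A reader might infer more than the documents support:

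- *That absence patients as a whole contribute nothing.* Both Seizures Subjects stay in the set. So do absence patients with O and E both below 4, by the second route in 5.6.
- *That everyone excluded was enrolled for absence seizures.* SAP 6.3.4 notes that the Absence Seizures Only set includes some subjects with fewer than 4 observable seizures per 4 weeks. Protocol inclusion criterion 4 accepts 2 in 4 weeks, so some may have qualified on observable seizures.
- *That subjects with no baseline absence seizures dilute the effect.* Percent reduction (5.7.3) is undefined at a zero baseline. The Absence Seizures set also admits subjects on EEG alone, with no diary absence entry.
- *That the diary is the stronger absence record because it covers weeks rather than a night.* Time covered is not detection. The protocol's Amendment 3 rationale ranks EEG as the most reliable method for absence seizures, and the primary and secondary absence endpoints use it.

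**Conclusion.** The point holds as an internal inconsistency with a definite consequence if Appendix A is followed. Every Absence Seizures Only Subject would then be left out of the four diary absence summaries and the related Week 8 p-values. The exclusion follows from the definitions and needs no assumption; the 8 to 16 subjects rest entirely on the assumed 20% to 40% share.

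The reach is limited. The primary endpoint uses the full Efficacy Analysis Set, and no secondary analysis draws on these rows. Diary absence data would be restricted, not lost. It is a minor correction, worth making because the choice of population should not remain open once treatment assignments are known.

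**What to change.** In Appendix A, change the eligible population for diary codes M to P to a set that includes Absence Seizures Only Subjects, and use that set in both Appendix A and Table 6. Either choice works:

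- **Efficacy Analysis Set.** This already matches the Table 6 title. Cost: four table cells.
- **Efficacy Analysis Set – Absence Seizures.** This matches the EEG absence rows. Table 6 has one title for all diary types, so codes M to P would need their own title. Cost: four cells and one title.

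State in 8.6.5 which set applies at Week 8, and whether the Week 52 summaries use the same set or the Extension Set named in 8.1. No new data or analysis method is needed. The change should be made before the Week 8 data are unblinded.
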